## Examination of First and Second Generation E-cigarettes

2. Risk of dual use of cigarettes and e-cigarettes: The concern of smokers engaging in dual use is that they will substantially increase their uptake of nicotine, leading to nicotine overdose. The symptoms of nicotine overdose include nausea, vomiting, dizziness, headache, and rapid heart rate. In our previous trial with e-cigarettes (see Preliminary Studies section), none of the participants reported any indication of nicotine overdose in their dual use of e-cigarettes and conventional cigarettes. In fact, most reduced their level of conventional cigarette use in proportion with their uptake of e-cigarettes. Preliminary analyses ( $n=20$ ) from another one of our current randomized trials investigating the use of ECs by caregiver's as a means of reducing their children's SHSe (i.e., parents asked to use EC anytime they are in the home, car, or around their child), indicate that caregivers decreased in their level of salivary cotinine ( $M_{baseline}=447.9$  to  $M_{3-mo}=314.8$ ). Caregivers also reported reduction in number of tobacco cigarettes per day from baseline to 3-month follow-up ( $M_{baseline}=19.6$  to  $M_{3-mo}=9.5$ ). Consistent with these findings, parents reported no adverse events, no serious adverse events, and specifically, no nicotine overdose event.
3. Loss of Confidentiality and Privacy: Confidentiality will be maintained by numerically coding all data, disguising identifying information, and keeping data locked in file drawers or in a secure, password protected database. All biospecimen samples are kept in a locked freezer and also will be deidentified. Names of participants will be kept separate from participant data. Only study research personnel and the PI will have the information that connects participants' names and ID numbers. All electronic data will be numerically coded and stored in a password-protected database, on a password-protected computer in a secure research space. Participant information will be accessible only to research staff, who are pledged to confidentiality and have completed training in the ethical conduct of research (i.e., both HIPAA and CITI trainings). Identifying information will not be reported in any publication.
4. Potential for Undermining Cessation: The study sample is comprised of smokers with no plan to quit in the next three months. Therefore, we are not asking smokers who want to quit to continue smoking. Moreover, our previous study of e-cigarette sampling and use among smokers unmotivated to quit smoking suggested that e-cigarette use increased smokers' readiness and confidence to quit smoking. At the end of the study, all participants will be debriefed and educated about ECs and conventional cigarettes. This education will include the information that: a) there is no safe cigarette, b) the best thing a smoker can do to improve health is to quit, c) some ECs are manufactured by the tobacco industry, d) ECs, though able to be regulated by the FDA as a tobacco product, are currently unregulated by the FDA until they are able to develop appropriate guidelines (based on research such as the present proposal), and e) it is unclear whether ECs reduce the risks associated with smoking. The PI will be available for any questions that participants may have about ECs, smoking, or smoking cessation. It is important to note that the use of ECs incurs no greater harm than if the participant decided on his/her own to use the product. ECs are available online and over-the-counter at various convenience stores, e-cigarette specialty stores and places where tobacco products are sold. Among those screened and ineligible/uninterested, referral resources for smoking cessation will be provided for those who inquire. Among study participants, information on cessation resources will be provided at the final visit and if at any time during the study participants are interested in smoking cessation services, a list of smoking cessation resources will be provided.
5. Lack of Appropriate Storage of EC Products: Consistent with [name] previous EC studies, participants will be instructed to keep their UBCs, EC cartridges and childproof e-liquid refill containers up and away from their children and pets to protect against unintentional poisoning. Although overdose or accidental ingestion is very unlikely and has not occurred in [name] previous studies, all participants will be provided the state and national poison control telephone line as well as a "tip sheet" on recognizing signs of nicotine overdose. It is important to note that in the

#### Examination of First and Second Generation E-cigarettes

unlikely event that someone other than the participant uses the EC, this risk would be no greater than if that same individual took the participant's cigarettes.

6. Slight risk of bruising, discomfort and infection with blood draw and oral (buccal) cell collection: Buccal cells and blood will be collected by trained research staff. Sterile instruments will be used and for blood draws, the participants skin will be cleaned with an alcohol wipe at the venipuncture site.

### **H. Data and Safety Monitoring Plan**

Adverse events will be assessed by study staff at each follow-up visit via participant self-report and managed immediately. All adverse events will be reported to the OSU IRB. We will monitor for risk of smoking by screening participants for general medical precautions (pregnancy, cardiovascular disease). Any adverse events, breaks of confidentiality, or any other data or safety issues that arise will be discussed immediately between study personnel and [name]. [name] will be responsible for completing an Adverse Events Form should an event occur. [name] will report potential unanticipated problems involving risks to subjects or others" (UPIRSOs) to the OSU IRB within 24 hours of having received notice of the event. [name] will gather any information needed to investigate the event and to determine subsequent action. Any subsequent action will be documented and reported to the OSU IRB and the Program Officer at NIH. Adverse event reports will be reviewed annually with the OSU IRB to ensure participant safety.

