### Counseling

Counseling as to use or not use the product at follow-up visits will not be a part of this study. At the second visit, participants randomized to ECs will be asked to attempt to completely switch to the product for the next 3 months. In subsequent visits, we will continue to ask participants to completely switch/stay switched but will not provide additional counseling (e.g., coping skills) so as to not influence the natural outcomes of product use (or non-use). For example, we assume that for those who find the product unhelpful in managing cravings or otherwise unsatisfying they will move on to another product or return to smoking. In real world use, most who try EC will not have access to a trained therapist who can effectively help them problem-solve such issues. We will provide participants trouble-shooting tips for the mechanics of their product, provide replacement parts as needed, and also address adverse events as they arise (though <2% and mild in [name] previous EC studies), but will not offer ways (e.g., timing, puff duration, etc.) to make the EC a better substitute or its use a more satisfying experience.

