## Outcome Measures

The following outcome measures will be assessed during study visits or emailed to the study participant if they are not able to attend a visit: 1) Complete Substitution will be defined as ≥7 days of no more than 1 conventional cigarette smoked (assessed via the *Timeline Follow Back Questionnaire* that assesses all tobacco/nicotine products used for prior 7 days), exhaled carbon monoxide of <4ppm (see biomarker measures below), and reported use of ECs over the same 7-day period; 2) EC Dependence will be assessed using an adapted version of the *Cigarette Dependence Scale* and the *Penn State EC Dependence Scale*; 3) Cigarette Dependence will be measured with the *Cigarette Dependence Scale*; 4) EC Likeability/Preference will be measured using items derived from the *Cigarette Evaluation Scale* (7-point Likert-type scale assessing different dimensions of responses to EC (e.g., psychological reward, satisfaction, and averseness) and an EC adapted version of the *Product Evaluation Scale*; 5) EC Abuse Liability will be assessed using both the *Drug Effects/Liking Questionnaire* as well as the *Cigarette Purchase Task* (modified to assess amount willing to pay across similar units of product, "How much would you be willing to pay for...a pack of your usual brand of cigarettes?...one e-cigarette cartridge?...1mL of e-liquid?"); 6) Transitions to other style of EC and tobacco products will be assessed by asking participants, "Have you tried any other e-cigarette devices since your last visit?" Affirmative responses will be followed-up with questions regarding type of product, frequency and duration of use; 7) Motivation Rulers: importance, confidence, and readiness to quit smoking and to quit all nicotine products (6-items total) will be collected to assess for changes in motivation over time.

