## Missing Data

In the event of missing data, we will contact participants immediately. If a participant drops out, we will attempt to gather follow-up information. However, if they refuse to be contacted or otherwise lose contact with the investigators, we will censor data at point of loss. Two statistical approaches will be used to handle missing data. First, we will use inverse probability weighting with propensity scores. This is a two-step procedure in which we first model the probability of missingness as a function of baseline covariates and previous outcomes. Next, the inverse of the resulting predicted probabilities (from the logistic regression model) serve as weights in our proposed model of the response (e.g., salivary cotinine at follow-up). We will compare these results to a more conservative intent to treat approach as a final step.

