### Protections Against Risk

Efforts to reduce risk are as follows:

1. Risk of using e-cigarettes: The risk of side effects and adverse events are very low. These products are sold online, and at e-cigarette specialty stores and convenience stores nationwide, without a prescription. Nevertheless, all participants will be screened for general medical precautions (pregnancy, cardiovascular disease) and monitored for adverse events during the study period. Study personnel will assess for adverse events via self-report at all follow-up visits. Smokers will also be provided a study phone line to report an adverse event between follow-up visits. Any serious adverse events will be reported to the PI and then to the OSU IRB and potentially to the NIH. We will withdraw participants who have a serious adverse event, or become pregnant or begin to breastfeed. The most likely adverse (potential for nicotine overdose) event is anticipated to be rare (<5% in [name] previous studies) and mild (nausea, headache, disrupted sleep) event will be handled quickly (i.e., advice to participant to reduce or stop EC use). [name], a physician, will also be available for medical oversight and to handle any questions regarding reported adverse events. Lab studies of toxin exposure suggest that ECs incur no greater risk to health than do conventional cigarettes. Indeed, e-cigarettes generally show lower levels of harmful and potentially harmful constituents. To date, five e-cigarette studies discuss adverse events (3 survey and 2 randomized clinical trials), reporting mild and tolerable side effects that generally resolved completely over time with continued use (90% of cases); the most predominant of which were mouth/throat irritation, cough, and headache. In both randomized clinical trials, no serious adverse events were reported and the e-cigarette group and the nicotine patch group had comparable levels of adverse events. The most common were mouth irritation, throat irritation, dry cough and headache.

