Study surveys that are able to be completed remotely will be sent to participants using their preferred method of contact prior to the scheduled in-lab study visit. Surveys will be considered complete if at least 90% of survey responses recorded are valid. Repetitive use of "Refuse to Answer", "0" or skipping of questions are not considered valid. Surveys completed remotely will be checked by research study staff. To receive the study visit portion of compensation, 90% of the survey responses recorded must be valid.

After each participant visit is complete, there will be at least a 45-minute period for cleaning and air exchanges in the negative pressure rooms and for cleaning exam rooms and equipment before the next participant visit. All smoking rooms are under negative pressure with a ventilation rate of 36.8 – 44.1 air changes per hour (ACH).

Examination of First and Second Generation E-cigarettes

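### When a follow-up visit is missed, outcome questionnaires are emailed but nobody is assigned to ask about adverse events, which leaves that time point to participant-initiated reporting

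*Combined protocol and SAP*

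**What the plan says.** Two sections describe how AEs are found, and both tie active questioning to visits. Section H (Data and Safety Monitoring Plan) says: "Adverse events will be assessed by study staff at each follow-up visit via participant self-report and managed immediately". Section G, Protections Against Risk, item 1, says: "Study personnel will assess for adverse events via self-report at all follow-up visits". It then adds a route outside visits: "Smokers will also be provided a study phone line to report an adverse event between follow-up visits". The Counseling section says that staff will "also address adverse events as they arise", but schedules no enquiry.

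Outcome data are treated differently. The Outcome Measures section lists seven measures, to be completed at visits or "emailed to the study participant if they are not able to attend a visit". AE questions are not among the seven. Table 3 has no AE row, and the diary variables described concern cigarettes, e-cigarette use and flavor. The biomarker modifier questionnaire asks about recent respiratory symptoms, but only at visits where specimens are taken.

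The Missing Data section promises contact: "In the event of missing data, we will contact participants immediately". It also foresees trying to obtain later information from people who drop out. It does not say that AEs are asked about in either case.

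**The concern.** The protocol expects some visits to be missed. It sets up an email route for that case, and the compliance bonus under Retention requires only seven of the eight visits. The route carries the smoking, dependence and liking questionnaires but no safety questions. A site that follows the text would collect self-reported outcomes from an absent participant and would not ask that person how they have been.

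What is at stake is mainly safety monitoring. The later steps depend on someone learning of the event: advice to the participant, the handling of serious events in section G, and the 24-hour report to the IRB, which runs from receipt of notice. Section G also describes an ongoing investigation of severe lung disease in people who vape. If AE rates are later reported by arm, attendance that differs between arms could make ascertainment differ too.

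**Working it through.** **Inputs.** Follow-up visits fall at weeks 1, 4, 8, 12, 26 and 52 (Design Overview). Enrollment is 453, that is 3 × 151 (Power Analysis). The documents state no missed-visit rate, no reasons for absence and no expected completeness of AE reporting, so there is no planned figure on this point to reproduce.

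**Step 1: is any active enquiry described for a missed visit?**

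| Place | What it provides | Active AE enquiry at a missed visit? |
|---|---|---|
| Section H | Staff ask at follow-up visits | No |
| Section G, item 1 | Staff ask at follow-up visits; phone line between them | No; the participant must call |
| Counseling | AEs dealt with as they come up | No enquiry scheduled |
| Outcome Measures | Seven measures emailed to absentees | No AE questions listed |
| Diary content and Table 3 | Smoking and product use; outcome schedule | No AE item |
| Missing Data | Contact when data are missing | Not stated |

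The gap is therefore between active and passive ascertainment at that time point.

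**Step 2: time between active enquiries when one visit is missed.** Interval = next visit attended minus last visit attended, with the neighboring visits both attended.

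| Visit missed | Calculation | Interval | Intervals if attended |
|---|---|---|---|
| Week 8 | 12 − 4 | 8 weeks | 4 and 4 |
| Week 12 | 26 − 8 | 18 weeks | 4 and 14 |
| Week 26 | 52 − 12 | 40 weeks | 14 and 26 |
| Week 52 | none later | no further enquiry | – |

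**Step 3: how many participants could be affected at one visit.** Number not actively asked = 453 × m, where m is an assumed missed-visit rate:

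- m = 5%: 453 × 0.05 = 22.65, about 23
- m = 10%: 453 × 0.10 = 45.3, about 45
- m = 20%: 453 × 0.20 = 90.6, about 91
- m = 30%: 453 × 0.30 = 135.9, about 136

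These count people not asked. They do not count events lost, because some events will be phoned in or recalled at the next visit, and the documents give no basis for estimating how many.

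**The case against.** The strongest reply is that the protocol already covers the period between visits. Participants have a phone line, staff deal with AEs as they come up, and missing data trigger prompt contact. AE procedures sit in sections G and H, so their absence from a list of outcome measures and from an outcome table proves little. The plan also refers to standard operating procedures and visit checklists that are not in the document and might include a telephone AE check. Much of this stands. It means a reader should not infer that absentees yield no safety data at all. It does not supply a scheduled enquiry: the phone line depends on the participant, and the missing-data contact names no AE questions.

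Other stronger readings are tempting but not supported.

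- **That absentees are the participants most likely to have been unwell.** This is plausible, but the documents give no reasons for missed visits.
- **That absentees still supply the trial's outcomes.** Only questionnaires can be emailed. Complete substitution also needs "exhaled carbon monoxide of <4ppm", and breath CO, specimens and spirometry are lost with the visit.
- **That the COVID-19 addendum is a second missed-visit route.** Its sentence beginning "Study surveys that are able to be completed remotely will be sent to participants" concerns surveys sent ahead of an in-person visit that still takes place.
- **That the 20% in the Power Analysis is the missed-visit rate.** It is attrition. People lost to contact would not return emailed forms either, so it cannot be turned into a share of events missed.
- **That the promise of immediate management cannot be kept.** It most naturally applies once an event is known.
- **That AE rates by arm are necessarily biased low.** This needs a link between illness and absence that the documents do not show. The Data Analytic Plan also contains no AE comparison by arm.

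**Conclusion.** The point holds in a limited form. As written, staff ask about AEs only at follow-up visits, while self-report outcomes have a remote route. A participant who misses a visit is not actively asked about AEs until the next one attended: 8, 18 or 40 weeks after the last enquiry if week 8, 12 or 26 is missed, and never again on schedule if week 52 is missed. The 40-week interval lies in the surveillance phase, when the trial no longer supplies e-cigarettes or e-liquid, though use is still being followed.

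The likely effect is later and less complete safety ascertainment. Its size is unknown. The range of about 23 to 136 of 453 participants per visit rests entirely on assumed missed-visit rates of 5% to 30%. The intervals assume a single missed visit and no AE enquiry laid down in procedures outside the document. The primary comparison is unaffected. This is a worthwhile, low-cost improvement to monitoring, not a flaw in the trial's main inference.

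**What to change.** In Outcome Measures, Protections Against Risk (item 1) and section H:

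1. Add the AE questions to the package emailed when a visit is missed.
2. Have existing staff telephone when the AE form is positive or not returned.
3. Record AE assessment as done or not done, by whatever route, at each scheduled time point, and tabulate this by arm.

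Item 3 makes incomplete ascertainment visible but does not by itself correct bias: a rate among those actually asked still leaves out those who were not. The recovery of information comes from items 1 and 2.

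The Measures section, which says that everything except the diary is collected on site, should be reconciled with the email route at the same time.

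The cost is one additional form in an existing email process and some staff time for calls. The downside is that self-completed AE forms are less detailed than a staff interview, which is why a positive answer needs a call. No dose, product supply or clinical rule changes.

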### Biomarkers of Toxicant Exposure

At visits where specimens are collected, participants will complete the Biomarker modifier questionnaire (used extensively in [name] current biomarker studies, a measure of factors that may moderate biomarkers of exposure and effect) which includes items that examine: a) tobacco smoke exposure at

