### Examination of First and Second Generation E-cigarettes

[figure not shown]
home, work and socially; b) frequency of alcohol and other drug use; c) perceived stress; d) recent respiratory symptoms; and e) current medications. Most biomarkers of exposure proposed in this study have been analyzed extensively in [name] laboratory. Methods for the analyses are described in the literature, and [name] possesses the expertise and laboratory capacity to conduct these analyses. The collected urine samples will be aliquoted into 5-mL cryovials, and each vial will be labeled with a unique ID encoding the study, subject, sample collection time-point, and the type of assay. Aliquots will be frozen at -20 °C until analyses are conducted. Saliva samples (up to 2-3 mL will be obtained to analyze for cotinine levels. We will also save additional aliquots for potential future analyses of biomarkers of exposure to other constituents identified in this Aim, or other biomarkers that may be developed over time. Blood samples will be collected into 'purple top' blood collection vacutainer tubes, and plasma, red blood cells, and buffy coat will be separated by centrifugation. Buffy coat (used to isolate DNA), plasma, and red blood cells will be stored at -80 °C for potential future studies. Urinary total NNN and total NNAL. Exposure to NNK—an accepted cause of lung cancer in smokers—is measured by urinary total 4-(methylnitrosamino)-1-(3-pyridyl)-1butanol (NNAL), which is the sum of NNAL and its glucuronides. This biomarker has been widely applied in studies of smoking and cancer, and its relationship to lung cancer in smokers has been demonstrated. Exposure to NNN, a well-established esophageal and oral carcinogen, is measured by the sum of urinary NNN and its glucuronide, referred to as total NNN. Urinary NNN is strongly related to the incidence of esophageal cancer in smokers. Only relatively small levels of NNN and NNK, have been reported to be present in EC fluids and aerosols. However, according to both the published literature and our preliminary data ([name], unpublished), there can be significant variation in the content of these carcinogens in EC and potentially variations between G1 and G2 products. Total NNN and total NNAL will be analyzed by liquid chromatography (LC)-tandem mass spectrometry (MS/MS) using standard validated methods. Briefly, urine samples will be mixed with stable isotope-labeled internal standards ([pyridine-D4]NNN and [C6]NNAL) and treated with β-glucuronidase to release free NNN and NNAL from their glucuronides. The samples will be further purified by solid-phase extraction and analyzed by LC-MS/MS monitoring transitions *m/z* 178 → 148 for NNN, *m/z* 184 → 154 for [C6]NNN, *m/z* 210 → 93 NNAL and *m/z* 216 → 98 for [C6]NNAL. Urinary HPMA. Acrolein exposure is measured by urinary 3-hydroxypropyl mercapturic acid (HPMA). Acrolein was chosen because it is an intense irritant and lung toxicant, and a suggested lung carcinogen that is present in EC. It will be analyzed using a validated method, in which purified samples will be analyzed by LC-MS/MS in the APCI mode, monitoring *m/z* 220 → 91 for 2-HPMA and 3-HPMA, and *m/z* 223 → 91 for [D3]3-HPMA (internal standard). *N*-HOMe-dAdo, and *N*-ethylidene-dGuo in leukocyte DNA. Exposure to formaldehyde and acetaldehyde can be measured via the analysis of *N*-hydroxymethyl-deoxyadenosine (*N*-HOMe-dAdo) and *N*-ethylidene-deoxyguanosine (*N*-ethylidene-dGuo), respectively, in human leukocyte DNA.

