*Hypothesis 2a:* The biomarker outcome measures analyzed will include mean levels of specific biomarkers at all follow-up time points. The analysis of biomarkers of toxicant exposure will be analyzed similar to outcome variables in Hypothesis 1b. Again mixed effects models will be used for analysis and resulting contrast estimates comparing group effects over time will be used as measure of effect. We will again apply a normalization transformation but will also include potential confounding factors measured in the

*Biomarker Modifier Questionnaire* in the model. *Hypothesis 2b:* Similar analyses to Hypothesis 2a will be performed but only among the subset of LWD and HWD users who completely switch.

**Aim 3:** The focus of Aim 3 is the examination of changes over time in biomarkers of toxicant effect (Hyp 3a) between LWD, HWD and UBC, and (Hyp 3b) amongst LWD vs. HWD users who completely switch. For Aim 3 (Hypothesis 3a and IRB NUMBER: 6379 3b), we will run the same analyses as in Aim 2, but the biomarker outcome measures analyzed will include mean levels of DNA damage and pulmonary functioning at all follow-ups.

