## **G. Human Participants**

### **Potential Risks**

The research protocol calls for current smokers who do not plan to quit smoking within the next three months to attempt to completely substitute a LWD e-cigarette, a HWD e-cigarette, or to continue to smoke their usual brand of cigarette as they wish. Participants will not be provided any more instructions for use, and non-use of e-cigarettes is a permissible outcome. E-cigarettes are no more harmful than conventional cigarettes, and there is some evidence that they may offer reduced harm. Questionnaires, exhaled breath and urine collection procedures are all non-invasive and involve minimal risk to study participants. Potential risks are as follows: a) risk of using e-cigarettes, b) dual use of cigarettes and e-cigarettes, c) loss of confidentiality or privacy, d) potential for undermining smoking cessation, e) lack of appropriate storage of nicotine-containing products in a house with children and pets, f) slight risk of discomfort, bruising and infection with blood draw, and g) slight risk of discomfort and very low risk of infection with oral (buccal) cell collection.

The Centers for Disease Control and Prevention (CDC), the Food and Drug Administration (FDA) and several states, and federal health departments are investigating a multi-state outbreak of severe lung disease associated with using e-cigarette/vaping products. The investigation is ongoing and has not identified a cause, but all cases have reported use of vaping devices. The majority of patients have reported vaping cannabis oil,

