### Examination of First and Second Generation E-cigarettes

such as THC, obtained on the black market or other sources. In addition, one of the chemicals that has been possibly linked is Vitamin E acetate (tocopheryl acetate) added to e-liquid cartridges and pods.

The FDA has advised consumers to protect themselves by not using vaping products of any kind obtained off the street or black market and to refrain from using THC oil or modifying/adding any substance to vaping products purchased at stores. We will recommend that participants use only the products that we provide them for this study and do not add any substances to the e-liquids or alter the device in anyway.

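### Adverse events are found only by participant self-report, while respiratory symptoms and spirometry collected at specimen visits have no stated route to the adverse-event record

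*Combined protocol and SAP*

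**What the plan says.** Section H states how harm is ascertained: "Adverse events will be assessed by study staff at each follow-up visit via participant self-report and managed immediately". Section G (Protections Against Risk, item 1) says the same for all follow-up visits, adds a phone line for reports between visits, and makes a physician available for medical oversight.

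Section G (Potential Risks) says that health authorities are "investigating a multi-state outbreak of severe lung disease associated with using e-cigarette/vaping products" and adds: "The investigation is ongoing and has not identified a cause, but all cases have reported use of vaping devices". It also says that most patients reported vaping cannabis oil and that Vitamin E acetate is a possible link. The response given is advice: "We will recommend that participants use only the products that we provide them for this study", without additives or alterations to the device.

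Two respiratory measures are collected for other purposes.

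- **Symptoms.** Under Biomarkers of Toxicant Exposure: "At visits where specimens are collected, participants will complete the Biomarker modifier questionnaire". It is described as a measure of factors that may moderate the biomarkers, and its items include "d) recent respiratory symptoms; and e) current medications".
- **Spirometry.** Under Other Biomarkers of Effect, a trained technician measures FEV1, FVC and their ratio. The Innovation text makes lung function a secondary health outcome. The Data Analytic Plan for Aim 3 says that the outcomes "will include mean levels of DNA damage and pulmonary functioning at all follow-ups".

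**The concern.** The plan singles out a lung hazard and collects two kinds of individual respiratory data, yet it does not say that anyone reads either of them for safety. The adverse-event record depends on what a participant says when asked, or chooses to phone in. A symptom ticked on the questionnaire, or a fall in FEV1 seen by the technician, has no stated path to the Adverse Events Form.

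What is at stake is the completeness of the safety record on the organ system that the plan itself highlights. The analysis does not make up for this. Models of mean levels compare arms and can hide individual declines, and the statistical section plans no adverse-event analysis. Section H provides for annual review of event reports with the IRB but mentions no tabulation by arm, so an imbalance between arms would not be visible in the planned output.

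**Working it through.** **Number of visits.** Two sources agree.

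- Retention section: specimen-visit payments total $100 at $20 each, so 100 / 20 = 5 visits.
- Table 3: the Pulmonary Function row has five marks. The columns are displaced in the available text, so only the count is used.

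The first specimen collection comes before randomization (Detailed Study Procedures, Baseline Phases 1 and 2), so 5 − 1 = 4 visits can show a change on product. The questionnaire has no row of its own in Table 3. Its timing follows from being given at specimen visits.

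**Data source against stated use.**

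| Data | Collected | Stated use | Stated route to the Adverse Events Form |
|---|---|---|---|
| Answer to staff enquiry | Six follow-ups (weeks 1, 4, 8, 12, 26, 52) | Safety | Yes |
| Phone report | Between visits | Safety | Yes |
| Respiratory-symptom items | Five specimen visits | Possible confounders in the Aim 2 and Aim 3 models | None |
| Spirometry | Five visits | Secondary outcome, mean levels | None |

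**What the self-report route can capture.** The two respiratory sources differ.

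- Symptoms: the participant is asked twice at the same visit, once by questionnaire and once by staff, so the staff enquiry will pick up some of them. No step compares the two answers.
- Spirometry: a numerical change is a technician's finding. A participant cannot feel a modest fall in FEV1 as such, so the stated route does not carry it.

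Under the COVID-19 addendum, surveys that can be done remotely are sent before the visit and accepted if 90% of responses are valid. That criterion concerns completeness, not content. The addendum does not say whether this questionnaire is among them.

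**Records concerned.** With 151 per arm (Power Analysis):

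- two e-cigarette arms: 151 × 2 = 302 participants; 302 × 4 = 1,208 post-baseline records per measure;
- with the plan's 20% attrition applied at every visit: 1,208 × 0.80 ≈ 966;
- still to be recruited: 453 − 220 = 233 (Recruitment section). With equal allocation, 233 × 2/3 ≈ 155 in the e-cigarette arms, and 155 × 4 = 620 records before attrition.

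These are planned records. The documents give no rate of new symptoms or of lung-function change, so the number of unrecorded events cannot be computed and could be zero.

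**The case against.** The strongest reply is that ascertainment is more active than it looks. Staff ask about adverse events at all six follow-ups, two more than the four post-baseline specimen visits, so everyone who answers the symptom items is also asked directly. Section G already names cough and throat irritation among the commonest effects in earlier studies. Key on-site personnel meet weekly and discuss data-monitoring results and concerns. Section H requires prompt discussion of any data or safety issue that arises. Visit checklists and standard operating procedures are promised and may contain a cross-check.

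Much of this stands, and it rules out several stronger readings.

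- A reader might infer that respiratory data would lie unseen until the final analysis. The weekly meetings and the general clause in section H do not support that. They are not a trigger, though: both act once someone has noticed an issue, and no stated step makes anyone look.
- A reader might infer that event counts will understate what participants reported. The documents show only that they can.
- A reader might infer that the plan predicts greater exposure in the whole high-wattage arm. The Innovation text speaks of greater exposure with these devices, but Hypothesis 2b limits the contrast to complete substituters. Hypotheses 1a and 2a expect more substitution with high-wattage devices and larger falls in exposure with more substitution.
- A reader might conclude that every worsened spirometry value should be logged. With no criterion, any numerical fall would qualify, and section H sends all adverse events to the IRB. That is unworkable.

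The operating procedures are not in the documents. If they already hold such a check, one sentence in section H settles that part of the point.

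**Conclusion.** The point holds as a gap in ascertainment. Adverse events come only from participant self-report, and no text links an individual's symptom answers or spirometry to the adverse-event record. A respiratory change can therefore be in the data set at any of four post-baseline visits without being recorded as an event. The gap is clearer for spirometry than for symptoms, because staff enquiry at the same visit covers some symptoms.

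Its size in events is unknown. The 1,208 planned e-cigarette-arm records (about 966 after attrition) show only how much existing data lacks a stated safety use. These counts assume 151 per arm, four post-baseline specimen visits per participant, and attrition applied equally throughout. The conclusion also assumes that no unseen operating procedure already makes the link. It is a worthwhile, inexpensive improvement. It is not evidence that harm is being missed, and it does not affect the primary comparison of complete substitution.

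**What to change.** Amend section H as follows.

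1. At each post-baseline specimen visit, in all three arms, staff compare the respiratory-symptom answers with baseline and with what the participant has just reported as adverse events. Any new or worsened symptom not already reported goes on the Adverse Events Form.
2. Individual spirometry results are made available to the physician who already provides medical oversight under section G. The physician judges whether a change is an adverse event.
3. Adverse events are tabulated by LWD, HWD and UBC in the annual review and in the final report.

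About half the sample was recruited before this protocol text, so the tables should distinguish events ascertained before and after the change.

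The cost is one checklist step per specimen visit, some physician review time, one table, and somewhat more events reported to the IRB. No new measurement is needed, and no clinical threshold or management rule is proposed.
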